information and health history. Women will receive a pregnancy test as part of the eligibility criteria for enrollment in the study. Vaginal samples will be collected to be analyzed for bacterial vaginosis, yeast, gonorrhea, trichomonas, and chlamydia. Samples will be collected again at the 6-week follow-up visit to conduct the same analyses. Pathology samples from Latin America will be sent to the Pathology Department at the Medical College of Wisconsin (Milwaukee, WI) for molecular analyses. The China samples will be analyzed in-country at both SDH and Hybribrio labs using molecular tests as well. In addition, the ability to pass the cervical swab used for vaginal samples into the endocervix will be recorded at both the pre-treatment and the six-week follow-up visits to gather information about treatment-induced stenosis. All women will also undergo HPV genotyping with next-generation sequencing. The specimen is taken prior to treatment to establish a baseline of which HPV types are present. If a different HPV type is present in the post-treatment specimen, this will be classified as a new rather than persistent infection. Evaluation of the HPV genotyping from Latin America will be conducted at the National Cancer Institute in the United States and in China, where these samples will be analyzed at local labs. All samples that are sent to the United States for analysis will be shipped using a specialized courier service.

All women will also undergo a pelvic exam and visual inspection of the cervix following placement of diluted acetic acid on the cervix. Women will be immediately withdrawn from the study if any of the following contraindications for cryotherapy are present on visual inspection 1) lesion extends to over 75% of the cervix, 2) lesion is too large to be covered by the cryotherapy probe, 3) lesion extends into the endocervical canal, 4) the cervix is distorted or has severe atrophy; 5) the cervix is not visible, 6) the squamo-columnar junction is not completely visible, 7) the cervix is hard to reach, and/or 8) suspicion of cancer. Women deemed ineligible for cryotherapy will undergo LEEP immediately. In the case of suspected cancer, women will be appropriately referred. Once a patient is deemed eligible for cryotherapy, the study coordinator at each site will log into REDCap (a secure, HIPAA-compliant web application for building and managing surveys and databases) to obtain the randomized treatment assignment.

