3.2 Sample size and statistical analyses

Treatment efficacy

Analytic Approach. The primary analysis will follow an "intent to treat" approach, and we will conduct an additional sub-analysis excluding patients referred to excisional treatments after randomization. Similarity of the two study arms in terms of follow-up rates, distribution of individual and demographic variables, and disease distributions will be assessed. We will calculate the cure fraction and the corresponding binomial 95% confidence interval (95% CI) of each treatment as the percentage of women diagnosed with CIN2+ at the twelve-month visit. The non-inferiority of the LMIC-adapted CryoPen[®] and the WISAP thermoablator relative to CO₂-based cryotherapy will be assessed by calculating 95% CIs for the differences (LMIC-adapted CryoPen® minus CO₂-based cryotherapy and WISAP thermoablator minus CO₂-based cryotherapy) in cure fractions. Non-inferiority will be concluded if the lower confidence bound is greater than the non-inferiority margin (-10%). Exploratory analysis of the effectiveness and differences between arms will be evaluated within strata defined by quartiles of age and by the baseline diagnosis. Both the local and expert pathologists' diagnoses will be used in these analyses. As warranted, a logistic regression model will be used to mutually control for all important variables and chance differences between study arms to identify the key determinants of treatment failure and differences (if any) in effectiveness between treatments.

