4.2 Inclusion and exclusion criteria

Women who present to the health facility for biopsy results and meet the study criteria will be invited to participate in the study. We will collect delinked, anonymous, pooled data (e.g., age, geographic area of residence, and diagnosis) on all women, including those who decline to participate, to characterize them and assess whether our study population is representative of the general population.

Criteria for Inclusion

- Women aged 18 and older
- Biopsy results of CIN2, CIN2-3, CIN3, or high-grade CIN not otherwise specified (quality assurance will be performed by an expert gynecologic pathologist)
- Willing and able to provide informed consent
- Willing and able to provide permanent or reliable address

Criteria for Exclusion

- Pregnant or plans to become pregnant during study
- History of total hysterectomy (verified by medical record or pelvic evaluation)
- Previous surgery destructive to the cervix within the last 5 years
- Patient not eligible for cryotherapy (1) lesion extends to over 75% of the cervix, 2) lesion is too large to be covered by the cryotherapy probe, 3) lesion extends into the endocervical canal, 4) the cervix is distorted or has severe atrophy; 5) the cervix is not visible, 6) the squamo-columnar junction is not completely visible, 7) the cervix is hard to reach, and/or 8) suspicion of cancer)
- Cervix shape disfigured or hard to reach

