5.0 Study procedures

5.1 Initial Exam

After a woman consents to participate in the research study and meets other eligibility criteria including testing negative on a pregnancy test, she will answer a short survey with demographic and life history information relevant to the study (i.e., age, location of residence relative to clinic, smoking and sexual history, parity and history of vaginal surgeries). Next, the provider will initiate the ablation procedure by performing a pelvic exam. If the provider determines during this exam that the condition of the cervix is not conducive to an ablation procedure for anatomical reasons, the participant will be removed from the study.

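### The primary non-inferiority comparison is a valid crude difference in cure fractions, but prespecifying adjustment for baseline grade, country and age would gain modest precision at little cost

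*Combined protocol and SAP*

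**What the plan says.** Section 3.2 (Treatment efficacy) states that non-inferiority "will be assessed by calculating 95% CIs for the differences" in cure fractions, each new device minus CO₂ cryotherapy. Non-inferiority is declared if the lower bound lies above -10 percentage points. The section does not use the word unadjusted. It is a fair inference, because no covariate, stratum or model is attached to this comparison.

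Age and baseline diagnosis do appear, but only for exploratory analysis "within strata defined by quartiles of age and by the baseline diagnosis". Adjustment is then described as follows: "As warranted, a logistic regression model will be used to mutually control for all important variables and chance differences between study arms". The stated purpose of that model is to find determinants of treatment failure and any differences in effectiveness between treatments. Its covariates are not listed.

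The candidate covariates are already in hand:
- **Grade:** section 4.2 admits "Biopsy results of CIN2, CIN2-3, CIN3, or high-grade CIN not otherwise specified", and section 3.1 bases the enrolment diagnosis on local pathology.
- **Age:** section 5.1 says that before the ablation "she will answer a short survey with demographic and life history information relevant to the study", and age is the first item listed.
- **Site:** section 3.1 names seven hospitals in three countries, and "the study coordinator at each site will log into REDCap" to obtain the assignment. No stratification factor for the randomisation is stated.

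**The concern.** The trial pools women across three countries and several lesion grades, and the plan itself treats age and baseline diagnosis as worth examining. If these variables predict cure, a comparison that ignores them has a wider confidence interval than necessary. In a non-inferiority trial that width counts directly against the margin.

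The adjusted model does not fill this role. Nothing says when it is warranted or which variables count as important, and part of its content depends on imbalances seen in the data. A logistic model reports odds ratios unless a further step is specified, and an odds ratio cannot be compared with a margin of -10 percentage points. Readers could be left with a second treatment estimate, on another scale and with covariates chosen late, beside the primary one.

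**Working it through.** **Inputs from section 3.2.** 307 evaluable women per arm (922 in total), margin 10 points, worst-case reference cure 50%, alpha 0.05, power at least 80%.

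**Reproducing the plan's power.** With equal true cure p in both arms, SE = √(2p(1−p)/307) and power = Φ(0.10/SE − z). At p = 0.50, SE = √(0.50/307) = 0.04036 and 0.10/SE = 2.478.
- One-sided 0.05 (z = 1.645): Φ(0.833) = 79.8%. The sample size for 80% power is 310 per arm, or 307 with a constrained-null variance. The stated figure is reproduced.
- Lower limit of a two-sided 95% interval (z = 1.960): Φ(0.518) = 69.8%. The sample size for 80% power is 393 per arm.

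So the stated power holds at one-sided 0.05 but not under the 95% interval rule. That mismatch is a separate matter; both bases are shown below.

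**Effect of adjustment.** If the covariates explain a share R² of outcome variance, the variance of the risk difference is multiplied by about (1 − R²), and the effective sample size is 307/(1 − R²). R² is assumed, since the documents give none. At 50% cure:

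| Assumed R² | Effective n per arm | 95% CI half-width (points) | Power, 95% CI rule | Power, one-sided 0.05 |
|---|---|---|---|---|
| 0 | 307 | 7.91 | 69.8% | 79.8% |
| 1% | 310 | 7.87 | 70.2% | 80.1% |
| 2% | 313 | 7.83 | 70.7% | 80.5% |
| 5% | 323 | 7.71 | 72.0% | 81.5% |
| 10% | 341 | 7.50 | 74.3% | 83.3% |

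Unrounded, R² of 1–10% moves power from 69.77% to 70.21–74.28% under the 95% rule (0.4 to 4.5 points). At one-sided 0.05 it moves from 79.76% to 80.11–83.32% (0.35 to 3.56 points). The equivalent in women is 310 − 307 = 3 to 341 − 307 = 34 per arm.

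**What R² might be.** For one binary factor with prevalence q and cure gap d, R² = q(1−q)d²/(p(1−p)).
- q of 30–50% and d of 10–20 points, at 50% cure: 0.8% to 4%.
- An assumed 60/40 split of CIN2 to CIN3, with cure of 75% versus 55% (overall 67%): 0.24 × 0.04/0.2211 = 4.3%.
- The same split, with 80% versus 50% (overall 68%): 0.24 × 0.09/0.2176 = 9.9%.
- The same split, with CIN3 at 77% (the lower end of the range in section 9.0) and 80% overall (section 3.2): CIN2 = (0.80 − 0.40 × 0.77)/0.60 = 82%, so d = 5 points and R² = 0.24 × 0.0025/0.16 = 0.4%. That is worth about one woman per arm.

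**Could adjustment restore 80% power under the 95% rule?** The required n is 0.50 × (1.960 + 0.842)²/0.01 = 392.4, so R² would have to be 1 − 307/392.4 = about 22%.

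**The case against.** The strongest reply is that nothing is broken. Randomisation makes the crude difference a valid estimate, on the same scale as the margin, with one stated decision rule. Adjustment corrects no bias and no type I error. All of that stands, and a reader who infers that the primary analysis is biased or invalid goes further than the documents allow.

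The size of the gain is also uncertain. R² of 5–10% needs a 20–30 point cure gap between grades, which the documents do not report. The few cure figures they give, from different sources, point if anything to a smaller gap. Grade is also a blunt covariate here, being a local reading that includes CIN2-3 and unspecified high-grade lesions. This stands, and is why the range above starts low.

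A reader might further infer that the logistic model is driven only by chance imbalance and could overturn the primary result. The text does not support that: it also refers to important variables, and the model lies outside the non-inferiority rule. What remains is narrower: no trigger, no covariate list and no link to the margin scale.

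Finally, adjustment is not wholly free. Seven hospitals crossed with several grades could produce sparse cells, so the covariates must be few and their grouping fixed in advance.

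**Conclusion.** The point holds as an efficiency and prespecification improvement, not as an error. The primary comparison ignores prognostic information that the trial already collects, and the one adjusted analysis is too loosely defined to supply it.

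For assumed R² of 1–10%, 307 per arm and 50% cure, the gain is worth about 3–34 women per arm: roughly 0.4–4.5 power points under the 95% interval rule, and slightly less at one-sided 0.05. It could be smaller still if grade separates outcomes poorly. The direction is secure, since a few prespecified covariates would not be expected to lose precision at this sample size. The size is not.

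It would be tempting to present adjustment as the remedy for the power shortfall under the 95% rule. The figures do not support this. An R² of about 22% would be needed, and the choice between one-sided 0.05 and a 95% interval must be resolved separately.

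**What to change.** In section 3.2, before outcome data are seen by arm:

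1. Make the primary estimate a standardised (marginal) risk difference. Fit a logistic model, predict cure for every woman under each arm, average the predictions and take the difference. Compare the lower limit of a delta-method or bootstrap interval with -10 points.
2. Fix the covariates: arm; local enrolment grade in a stated grouping (for example CIN2 versus CIN2-3, CIN3 and unspecified high-grade together); country rather than individual hospital, to avoid sparse cells; and age as a continuous variable.
3. Keep the crude difference and its interval as a sensitivity analysis.
4. Use the same list in place of the open-ended wording on the logistic model. Label any wider search for determinants of failure as exploratory.

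The cost is one analysis plan paragraph and minor programming. No new data and no change to recruitment are needed.

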Statistical Power and Sample Size. With a total of 922 women with a diagnosis of CIN2+, 307 per treatment arm, the study will have at least 80% power (alpha = 0.05) to detect a non-inferiority margin difference of 10% between the cure fraction of CO₂-based cryotherapy (reference) and of the LMIC-adapted CryoPen® (experimental) and the WISAP thermoablator (experimental), for a range of efficacy (50% to 80%) for the reference treatment and 40% efficacy under the null hypothesis of inferiority. We chose a range of 50-80% efficacy for cryotherapy because although the literature suggests CO₂-based cryotherapy is 80% effective, the disease ascertainment by colposcopy following treatment in previous studies was before the recognition that colposcopy is not perfectly sensitive. Therefore, the disease ascertainment in those studies was not as rigorous as proposed in this study. To ensure that the study is sufficiently powered for a wide range of efficacies, we are selecting 50% efficacy for the control arm as the worst-case scenario for study power. In order to achieve a sample size of 922 with complete follow-up, we will enroll 1281 women with CIN2+ under the assumption that 10% will have contraindications for cryotherapy and 20% will be lost to follow-up at twelve months post-treatment.

Test of cure

Analytic Approach. Since all women returning for the twelve-month visit will undergo four-quadrant biopsies and LEEP if diagnosed with CIN2+, regardless of the baseline characteristics or ablative treatment, we can assess the test of cure performance (sensitivity, specificity, positive predictive values (PPV), and negative predictive values (NPV)) of each test (VIA, cytology, and high-risk HPV DNA) for recurrent CIN2+ and CIN3 diagnosed by local and expert pathology. Performance will be stratified by quartiles of age and by the baseline diagnosis. McNemar chi-square will be used to test whether differences in sensitivity and specificity are significant (p < 0.05). A method developed by Leisenring *et al.* ¹² will be used to test for significant differences in PPV and NPV.

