Statistical Power. The statistical power for comparing sensitivity for the test of cure for VIA, cytology, and high-risk HPV testing is dependent on sample size of the efficacy study and the actual efficacy. We are enrolling 1281 women to assure that we have 930 women with a twelve-month follow-up. The larger the number of women who return for their follow-up, the larger the sample size for a given level of efficacy will be. The more efficacious the treatments, the smaller the sample size will be. Assuming 70% efficacy in treatment (30% recurrence), results of tests for cure will be available for 279 women with recurrence. This will provide 85% power (0.05 two-sided alpha) to detect a 10% difference in sensitivity between tests assuming 20% discordance between tests.

Interim Analysis of Cure Fractions. An interim analysis of cure fractions will be performed after approximately 2 years of study opening, when approximately 1/3 of the women have been enrolled. A confidence interval will be calculated for the difference (LMIC-adapted CryoPen® minus CO₂-based cryotherapy and WISAP thermoablator minus CO₂-based cryotherapy) in cure fractions. If the upper bound of the confidence interval is lower than the non-inferiority margin (-10%), then treatment modification or termination may be considered. The confidence interval will be calculated using an alpha calculated using an alpha time-squared spending function to maintain an overall 5% Type I error (one-sided).

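### 307 women per arm give about 80% power only at one-sided 5%; under the plan's 95% CI rule, power is about 70% at the 50% control cure rate chosen as the worst case

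*Combined protocol and SAP*

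**What the plan says.** All the relevant text is in the combined protocol and SAP, mainly section 3.2.

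- **Decision rule (Treatment efficacy, Analytic Approach).** Non-inferiority of each device to CO₂ cryotherapy "will be assessed by calculating 95% CIs for the differences" in cure fraction. The criterion is: "Non-inferiority will be concluded if the lower confidence bound is greater than the non-inferiority margin (-10" percentage points). The same paragraph uses the term 95% CI for the ordinary interval around each arm's cure fraction.
- **Power (Statistical Power and Sample Size).** With 922 women in total, "307 per treatment arm, the study will have at least 80% power (alpha = 0.05) to detect a non-inferiority margin difference of 10" percentage points. This is claimed "for a range of efficacy (50% to 80%) for the reference treatment". The section then says "we are selecting 50% efficacy for the control arm as the worst-case scenario for study power". It does not say whether alpha is one-sided or two-sided.
- **Evaluable total (Test of cure, Statistical Power).** "We are enrolling 1281 women to assure that we have 930 women with a twelve-month follow-up". Figure 1 in section 3.1 also shows 930 at 12 months. The power for this secondary question does state its sidedness: "This will provide 85% power (0.05 two-sided alpha").
- **Interim analysis (section 3.2, repeated in section 12.0).** Treatment modification or termination may be considered on this condition: "If the upper bound of the confidence interval is lower than the non-inferiority margin (-10" percentage points). An overall one-sided 5% Type I error is stated here, and only here.

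**The concern.** A 95% CI is two-sided unless the text says otherwise, so using its lower limit is a one-sided 2.5% test. If the sample size was worked out at one-sided 5%, the power statement describes an easier test than the one the trial will apply.

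Two things are at stake. First, the trial may have clearly less power than stated at the cure rate chosen for sizing. That rate matters because the plan argues that its more rigorous ascertainment may show lower cure than the published 80%. Second, whether a 90% or a 95% two-sided interval is used can decide if a device is declared non-inferior, so the choice must not stay open until data are seen.

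**Working it through.** **Inputs (section 3.2)**
- Evaluable women: 922, or 307 per arm. Check: 1,281 × 0.9 × 0.8 = 922.3, and 922.3/3 = 307.4.
- Margin: 10 percentage points on the cure difference.
- Control cure p: 50% to 80%, with 50% as the worst case.
- Assumption: true difference of 0. The plan does not say this in words, but it gives 40% as the cure rate under the null, which is 50% minus the margin.

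**Formulas** (unpooled variance, equal true cure rates)
- Power = Φ(0.10/√(2p(1−p)/n) − z)
- n per arm for 80% power = (z + 0.8416)² × 2p(1−p)/0.10²
- z = 1.645 for one-sided 5%; z = 1.960 for the lower limit of a two-sided 95% CI.

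**Step 1: reproduce the plan's figure at p = 0.50**
- One-sided 5%: n = (1.645 + 0.8416)² × 0.50/0.01 = 309.1, so 310 per arm and 310 × 3 = 930. That equals the 930 in Figure 1 and in the test-of-cure paragraph.
- At n = 307 the standard error is √(0.50/307) = 0.04036, so 0.10/0.04036 = 2.478. Power = Φ(2.478 − 1.645) = Φ(0.833) = 79.8%.
- One-sided 2.5%: n = (1.960 + 0.8416)² × 0.50/0.01 = 392.4, so 393 per arm. The plan's size does not reproduce.

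Only one-sided 5% gives the stated 80% at 50% cure.

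**Step 2: apply the written decision rule at p = 0.50**

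Power = Φ(2.478 − 1.960) = Φ(0.518) = 69.8%.

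**Step 3: the whole claimed range, 307 per arm, each comparison separately**

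| Control cure | 95% CI rule | 95% CI rule, exact | One-sided 5% |
|---|---|---|---|
| 50% | 69.8% | 70.0% | 79.8% |
| 60% | 71.5% | 71.3% | 81.2% |
| 70% | 77.2% | 77.3% | 85.5% |
| 75% | 81.6% | 81.7% | 88.8% |
| 80% | 87.2% | 87.3% | 92.7% |

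The exact column enumerates the binomial outcomes under a Wald interval.

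**Step 4: where the claim starts to hold**

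80% power needs 0.10/SE = 1.960 + 0.8416 = 2.8016, so SE = 0.03569. Then p(1−p) = 307 × 0.03569²/2 = 0.1956, which gives p = 0.733.

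**Step 5: sensitivity**
- With 310 per arm: 70.2% (95% CI) and 80.1% (one-sided 5%) at 50% cure, with the 80% crossing at 72.9%.
- With the null variance taken at 50% versus 40%: 70.5% and 80.2%.
- With the Farrington-Manning variance: 70.1% and 80.0%, with the crossing at 73.4%.

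The choice of method does not explain the gap.

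**Step 6: scale of the shortfall in women**

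80% power at 50% cure under the 95% CI needs 393 × 3 = 1,179 with complete data. With the plan's own losses, 1,179/0.8/0.9 = 1,637.5, so about 1,638 enrolled instead of 1,281.

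**The case against.** The strongest counter-reading is that the plan means one-sided 5% throughout. The interim text speaks of an overall one-sided 5% error, and with a spending function that word usually covers the final look too. The decision rule looks at one bound only. If that bound is a one-sided 95% limit, power runs from 79.8% to 92.7% over the claimed range and the statement essentially holds.

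This makes one-sided 5% a plausible sizing assumption, but it does not remove the conflict. No passage calls the final interval one-sided, and the same paragraph uses 95% CI for the plain per-arm intervals. The interim rule uses the upper bound to flag inferiority, which is a different error from a false non-inferiority claim at the end. If alpha 0.05 was instead meant as two-sided, the error rates agree, but the power figure is then about 10 points too high at 50% cure.

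Some points on the other side do stand:
- The 95% CI as written is the stricter rule and does not raise the risk of a false claim.
- At the 80% literature value cited in section 3.2, power is 87.2%. At 77%, the low end of the CIN3 range in section 9.0, it is 84%.
- Between about 71% and 73% cure the shortfall is 2 points or less.
- The 70% efficacy in the test-of-cure paragraph is an assumption across all arms, not a design value for the control arm.
- That 930 came from a one-sided 5% calculation is inferred from the match; the plan does not say so.

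**Conclusion.** The concern holds. As written, the decision rule and the power statement cannot both stand. Under the 95% CI rule, the claim of at least 80% power is true for control cure from about 73% to 80% and false from 50% to about 73%. At the 50% worst case the chance of missing an equally effective device is about 30% per comparison instead of 20%; at 70% cure it is about 23%.

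This rests on reading the 95% CI as two-sided, on equal true cure rates, and on 307 evaluable women per arm with each comparison taken separately. The harm is lost power and a wrong stated figure, not a looser standard for non-inferiority. It must be fixed because it concerns the error rate of the primary test at the plan's own design point.

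**What to change.** **Preferred.** Keep the 95% CI. In section 3.2, state one-sided alpha = 0.025 for the final non-inferiority test in both the Analytic Approach and the Statistical Power and Sample Size paragraphs. Replace the blanket power claim with power per comparison at 307 per arm and equal true cure rates: about 70% at 50% control cure, 71.5% at 60%, 77% at 70%, 82% at 75% and 87% at 80%.

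**Alternative, if one-sided 5% was intended.** Say so before data are seen, change the decision rule to a one-sided 95% lower bound (equivalently a 90% two-sided CI), and state power as about 80% at 50% cure.

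In either case the interim alpha in sections 3.2 and 12.0 can stay, since it governs the inferiority flag. Naming the final test explicitly prevents the two from being confused.

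**Cost.** Wording in two paragraphs of section 3.2. No extra women and no change to the interim boundary. Under the preferred option the stated power becomes less favourable. The 1,638 enrolled is given for scale only, not as a request.

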The single or double freeze modalities were chosen given the results of the UH2 trial where single-freeze CryoPen® achieved a greater depth of necrosis than double freeze, and the WHO cryotherapy guidelines which endorse CO₂ double-freeze as the standard cryotherapy treatment. While these are the preferred modalities, in a few cases clinicians may decide to repeat the CryoPen® modality to correct placement of the first application and maximize treatment efficacy and patient safety.

We will approach approximately 1,602 women with CIN2+ during a 2.5 year enrollment phase (30 months). Assuming an approximately 80% participation rate, ¹⁰ approximately 1,281 women will be enrolled—1,152 (90%) will be eligible for cryotherapy (i.e. no contraindications) and 129 will be ineligible and undergo alternative treatments. We estimate that approximately 20% will be lost to follow-up at the twelve-month visit, so that we will have complete data on a total of 922 women (57.5% of 1,602) treated with either CO₂-based cryotherapy, LMIC-adapted CryoPen®, or thermoablation. We will monitor the percentages of ineligibles, contraindications, and loss to follow-up in real time and adjust recruitment accordingly to achieve the target sample size. In addition, we will conduct a non-essential 6-week follow-up visit to evaluate adverse effects from the ablative procedures. The primary endpoint of the study will be to determine residual disease at a 12-month follow up visit as determined by colposcopy and four-quadrant biopsies.

Enrollment and Treatment

Enrollment diagnosis will be based on the local pathology. These slides will be read by an expert gynecologic pathologist for quality assurance. At the pre-treatment visit, consented women will be administered a short questionnaire to collect demographic

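### Section 3.2 ties two completer counts, 922 and 930, to the same 1,281 women; only 922 follows from the stated losses, so the 930 and the 279 recurrences built on it need a minor correction

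*Combined protocol and SAP*

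**What the plan says.** The plan gives the number of women with 12-month data in four places.

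- **Section 3.1, text.** About 1,602 women are approached. At 80% participation 1,281 enrol, and of these "1,152 (90%) will be eligible for cryotherapy". It then assumes that "approximately 20% will be lost to follow-up at the twelve-month visit", "so that we will have complete data on a total of 922 women".
- **Section 3.2, primary sample size.** The paragraph works with 307 women per arm and says "In order to achieve a sample size of 922 with complete follow-up, we will enroll 1281 women with CIN2"+, giving the same 10% contraindication and 20% loss as the reason.
- **Section 3.2, test-of-cure power.** "We are enrolling 1281 women to assure that we have 930 women with a twelve-month follow-up". Assuming 70% efficacy, it continues that "results of tests for cure will be available for 279 women with recurrence", and claims 85% power for a 10% difference in sensitivity.
- **Figure 1.** The flow chart shows 1,602 women with CIN2+, 1,152 randomised and 930 at the 12-month follow-up.

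The difference between 922 and 930 is not explained anywhere.

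**The concern.** Two paragraphs of one section start from the same enrolment and arrive at different numbers of completers. Both cannot follow from one set of loss assumptions. The larger number is also used further on: it is the base for the expected recurrences, which are the effective sample size for comparing the sensitivity of VIA, cytology and HPV testing.

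At stake is whether the power statements rest on a sample that the plan expects to obtain. There is also a practical side. Section 3.1 commits the team to monitoring losses and adjusting recruitment to reach the target, and anyone checking completion against Figure 1 would use a different number from someone using the text.

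**Working it through.** **Inputs.** Approached 1,602, participation 80%, eligible 90%, loss 20% (section 3.1; the 10% and 20% are repeated in section 3.2). Recurrence 30%, sensitivity difference 10%, discordance 20%, two-sided alpha 0.05 (section 3.2, test of cure). Margin 10 points and worst-case control cure fraction 50% (section 3.2, treatment efficacy).

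**1. Reproduce the plan's chain.**
- Enrolled: 1,602 x 0.80 = 1,281.6; the plan has 1,281.
- Eligible: 1,281 x 0.90 = 1,152.9; the plan has 1,152.
- Completers: 1,152 x 0.80 = 921.6, or 922. Per arm: 922 / 3 = 307.3, or 307.

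The 922 and the 307 are reproduced.

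**2. What 930 would need.**
- From 1,152 randomised: 1 - 930/1,152 = 19.3% loss instead of 20%.
- At the stated rates: 930 / 0.80 = 1,162.5 (1,163 randomised), and 1,162.5 / 0.90 = 1,291.7 (1,292 enrolled). That is 11 more than planned in each count.
- The excess over 922 is 8 women: 8/922 = 0.9%.

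**3. Recurrences.** 0.30 x 930 = 279, so 279 is correct arithmetic on 930. On 922 it is 0.30 x 922 = 276.6, or 277.

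**4. Effect on test-of-cure power.** McNemar comparison, normal approximation: power = Φ[(d√n - 1.96√ψ) / √(ψ - d²)], with d = 0.10 and ψ the total proportion of discordant pairs. The plan does not say whether its 20% is the total or one discordant cell, so both readings are shown.

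| Reading of 20% | ψ | n = 279 | n = 277 |
|---|---|---|---|
| Total discordance | 0.20 | 96.6% | 96.5% |
| Larger cell, with the smaller 10% | 0.30 | 86.6% | 86.4% |

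The exact test gives 96.3% and 96.2% in the first row, and 84.7% and 84.4% in the second. The change is therefore 0.1 to 0.2 points by the approximation, and at most 0.3 by the exact test. Only the second reading comes close to the plan's 85%.

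**5. Effect on worst-case primary power.** Both cure fractions are taken as 50%, with margin 10 points. One-sided alpha 0.05 is assumed, because the paragraph gives only alpha = 0.05. Power = Φ[0.10 / √(2 x 0.5 x 0.5 / n) - 1.645].
- n = 307: Φ(2.478 - 1.645) = 79.8%.
- n = 310 (930/3): Φ(2.490 - 1.645) = 80.1%.
- If the critical value instead uses the null variance at 50% against 40%, n = 307 gives Φ[(0.10 - 1.645√(0.49/307)) / √(0.50/307)] = 80.2%.

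**The case against.** The strongest reply is that this is too small to matter. Section 3.1 labels its counts and the 20% loss as approximate, 930 needs only 19.3% loss, and losses are monitored as the trial runs. That stands as a limit on the size of the point. It does not remove the inconsistency, since the test-of-cure paragraph states 930 as something that enrolling 1,281 will secure.

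A reader might go further than the documents allow, in four ways.

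- **That the recruitment target is wrong.** It is not. The figure of 1,281 is what the stated rates require for 922.
- **That the trial has two competing recruitment targets.** The commitment to adjust recruitment comes shortly after the 922 in section 3.1, and the primary sample-size paragraph also names 922. The 930 appears only in Figure 1 and in a secondary power statement. No text directs recruitment to it.
- **That 930 is out of reach.** A loss slightly under 20% would deliver it.
- **That the test-of-cure comparison loses its power.** Two fewer recurrences change nothing of substance.

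It can also be argued that 930 is the better number, since 310 per arm passes 80% in the simple worst-case calculation and 307 falls just short. This deserves weight when the text is corrected. However, it depends on an assumed one-sided alpha and on the variance formula, and the documents do not say that 930 arose as 3 x 310.

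**Conclusion.** The inconsistency is real and minor. Under the plan's own 10% and 20% losses, 1,281 enrolled gives 922 completers. The 930 in Figure 1 and in the test-of-cure paragraph, and the 279 recurrences taken from it, do not follow. The overstatement is 8 completers and 2 recurrences. Enrolment stays as planned, and no conclusion about power changes.

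The completer arithmetic needs only the stated rates. The power figures rest on two assumptions: how the 20% discordance is read, and a one-sided alpha of 0.05 for the primary comparison. On the second, the choice of 922 touches the claim of at least 80% power at 50% cure, which becomes 79.8% or 80.2% depending on the variance used. Two neighbouring matters are separate from this point and are not settled here: the meaning of the discordance figure, and the sidedness of the primary alpha. If the two-sided 95% interval in section 3.2 sets the level, the simple formula gives about 70% at either 307 or 310 per arm.

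**What to change.** Use one completer count throughout:

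- In Figure 1 and in the test-of-cure power paragraph, replace 930 by 922 (307 per arm).
- In the same paragraph, replace 279 recurrences by 277.
- Restate the test-of-cure power from 277, and say whether the 20% is total discordance or one cell, since the result depends on it.
- Restate the worst-case primary power at 307 per arm, giving the sidedness of alpha and the variance formula. By the simple approximation with one-sided 0.05 it is about 79.8%.

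The cost is a few figures in the text and one figure label, with no extra patients. The downside is slightly less favourable stated figures. If the sponsor prefers to keep 930, the stated rates call for about 1,292 enrolled, 11 more women than planned.
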